7.4. Statistical Analyses

The Statistical Analysis Plan (SAP) will be developed and finalized before database lock of the interim analysis and will describe the participant populations to be included in the analyses, and procedures for accounting for missing, unused, and spurious data. This section is a summary of the planned statistical analyses of the primary and secondary endpoints considering all relevant aspects of the FDA Guidance for Industry (E9) Statistical Principles for Clinical Trials (FDA Guidance for Industry E9 Statistical Principles for Clinical Trials, 1998).

7.4.1. Demographics and Baseline Characteristics

Disposition, demographics, medical history, prior/concomitant medication, and compliance will be displayed in a descriptive manner. Further details will be provided in the SAP.

7.4.2. Efficacy Analyses

The **primary efficacy** endpoint, the percentage of patients with at least one COVID-19–related medically attended contact, due to increased symptom severity or death (all-cause mortality) through Day 30, will be analyzed using a two group χ^2 test with pooled variances and no continuity correction. Statistics and the associated 95% confidence interval will be provided. The primary efficacy analysis will be performed using the ITT and will be repeated for robustness purposes with the PP.

In case of missing data of the primary endpoint at day 30 (Visit 4), the primary analysis will consider participants (with missing primary endpoint data until day 30) as having at least one medically attended visit. For sensitivity purposes, the primary efficacy analysis will be repeated by excluding participants with missing primary endpoint until day 30 (Complete Case Analysis).

The **secondary safety endpoints**: Incidence of Related Serious Adverse Events (SAE), Incidence of discontinuation due to related SAE and Incidence of death will also be analyzed using a χ^2 test. Descriptive statistics including exploratory confidence intervals/p-values will be provided.

All **other efficacy endpoints** will be analyzed in an exploratory manner by applying appropriate statistical methods (e.g. χ^2 test for incidences, log rank test and Kaplan Meier method for cumulative incidences, ANOVA for continuous variables) using the FAS set. Descriptive statistics including exploratory confidence intervals/p-values will be delivered.

All **other safety related endpoints** will be analyzed in a descriptive way by providing descriptive statistics and/or shift tables from baseline to the assessment visits.

For more details of the statistical analysis, methods/models refer to the SAP.

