Statistical Methods: The study will aim to enroll up to 1465 participants, which assumes a 10% screen failure rate, with a final allocation of 659 participants in the treatment arm and 659 in the control arm.

This sample size of ensures a power of 90% at a 2-sided α of 5%, assuming a 1:1 randomization, a placebo rate of 6% (of participants with at least one COVID-19–related medically attended contact, due to increased symptom severity, or incidence of death due to COVID-19 through Day 30) and an assumed relative risk reduction of 65% to 2.4% in the active treatment arms. The statistical test of the null hypothesis of no between-group difference in proportions, as specified

in the primary endpoint, will be tested using a χ^2 test at a two-sided 5% significance level. An interim analysis for futility will be performed after 50% of participants have completed the primary endpoint assessment at day 30. Safety analyses will be performed on the Safety Population, consisting of all participants who are randomized and received study drug, analyzed by actual treatment arm. A more detailed description of the statistical methods can be found in Section 7.

Protocol Title: A virtual Phase 2 randomized, placebo-controlled, double-blind study to evaluate the safety and efficacy of the combination of famotidine and celecoxib as a post-exposure prophylaxis (PEP) for newly-infected COVID-19 patients.

Short Title: LEAP-CT as a post-exposure prophylaxis for newly-infected COVID-19 patients.

Rationale: Please refer to the Master Protocol LDOS-21-001 for a comprehensive background and rationale for this study of a combination of famotidine and celecoxib as post-exposure prophylaxis (PEP) for newly-infected COVID-19 patients.

Overall Design: This is a Phase 2, randomized double-blind placebo-controlled decentralized virtual study in which outpatient participants, newly diagnosed for COVID-19, will be randomized in a 1:1 ratio to one of two study groups (1 treatment group and 1 control group). The study is designed as a virtual trial in that it will be conducted, *in situ*, with home-based participants entering self-assessments via a web-enabled adaptive platform – The participants will be under the oversight of regionally based investigators who will be responsible for study conduct and the review of blinded data on a periodic basis.

Intervention Groups and Duration: The treatment regimen for this study is shown in Table 4.

Regimen	Dose	# of Participants

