Study Day		Day 1 Baseline/ Start of Treatment ⁴	Day 7(±1)	Day 14 (±1)	Day 30(±1) End of Treatment	Day 60	Day 90
Informed consent ⁵	Х						
Inclusion and Exclusion criteria	Х	Х					
Demographics	Х						
Medical History, including weight reporting ⁶	X						
Concomitant medication review	X	X	X	X	Х		
Blood draw for comprehensive metabolic panel (mobile phlebotomy & laboratory service)	Х		X	X			
Nasal swab for confirmatory PCR test for at-home antigen positive test prescreened participants (mobile phlebotomy & laboratory service)	X						
Randomization and initiation of drug shipment ⁷	Х						
Review of reported baseline symptoms		Х		X			
Confirmation of Study Drug Receipt & Initial Dose		X					
Confirmation of Study Drug Return Shipment ⁸					Х		
Review of eDiary for study drug compliance ⁹			X	X	Х		
Adverse Events Review		X	X	X	Х		
Participant Intake of study drug		Daily on Day	s 1–14				

Study Activities and Assessments	Screening & Randomization ¹		Treatment Po	eriod		Observati	on Period ²
Visit Number ³	1	2	3	4	5	6	7
Study Day		Day 1 Baseline/ Start of Treatment ⁴	Day 7(±1)	Day 14 (±1)	Day 30(±1) End of Treatment	Day 60	Day 90
Symptom questionnaires, spO2, and temperature		Daily for the entire treatment and observation period (Days 1–90)					
Mobile ECG		Х	Х	Х			

¹ Participant will complete demography, medical history, concomitant medications, and questions regarding inclusion and exclusion criteria [including results of SARS-CoV-2 PCR test and self-administered urine pregnancy test] via Site will review participant responses and confirm information with participant by Visit 2.

² During the observational period, while participant is not taking any IP, participant will record long term symptoms for Covid-19, but will be directed to consult with his/her primary care physician (PCP) for follow up of any health changes. Planned contacts with participants on Days 60 and 90 will be performed by study support staff only to confirm continued participation in the study.

³All participant visit activities will be performed remotely.

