7.2. Sample Size Determination

The sample size was estimated assuming that an interim analysis with stopping criteria for futility will be performed after 50% of participants have a primary endpoint assessment at Day 30. The O'Brien-Fleming beta-spending function is used to determine the non-binding futility boundary.

A total of 1318 evaluable participants, defined as part of the Full Analysis population (659 per group) are required to detect a relative reduction in the primary efficacy parameter of 60% in the active treatment arms compared to placebo (from of 6% in the placebo group to 2.4% in the active groups) with 90.0% power and using a two-sided χ^2 -test with 0.5% significance level, assuming variances are pooled, and that continuity correction was not used. Assuming a 10% screen failure rate, 1465 enrolled participants will be required.

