7.4.3. Interim Analyses

An interim analysis with stopping criteria for futility and validation of sample size is planned after 50% of the participants have completed the primary endpoint assessment at Day 30 (Visit 4).

To prevent power loss due to this interim analysis, a beta-spending function was used to calculate stopping bound according to O'Brien and Fleming (Lan, 1983) (O'Brien, 1979). The futility bound for difference in proportions between active treatments and placebo is 0.0232 in the interim analysis. The nominal level of significance is not affected α =0.05 (two-sided) and 90% power is kept for the final analysis. The interim analysis will be performed on the Full Analysis set.

If the primary endpoint is missing at Day 30, the participant will be excluded from the interim analysis (Complete Case Analysis). The interim efficacy analysis will be performed using a two-group chi-square test comparing the FCI combination with placebo followed by the FC–placebo comparison.

If the study is not stopped due to futility after the interim look, the assumptions for the sample size determination will be checked and the sample size may be increased if a decrease in treatment difference by more than 10% (due to a lower placebo rate and/or due to a higher rate in the active arms) is observed.

The SAP will describe the planned interim analyses in greater detail.

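### The primary chi-square is valid and adequately powered, but it leaves baseline age and symptom severity unused; a standardised risk difference would give a small, low-cost gain in precision

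*Protocol*

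**What the plan says.** Section 7.4.2 names the primary analysis outright: a two-group chi-square "test with pooled variances and no continuity correction" on the proportion with at least one COVID-19-related medically attended contact, or death, through Day 30. Its two companion analyses, the per-protocol repeat and the complete-case analysis, repeat that analysis, so neither is adjusted. Participants with a missing primary endpoint count as events in the primary analysis.

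The sample size in Section 7.2 uses the same test, "assuming variances are pooled, and that continuity correction was not used", for a fall from "6% in the placebo group to 2.4% in the active groups" "with 90.0% power". The Synopsis also says the hypothesis is "tested using a χ^2 test at a two-sided 5% significance level".

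Baseline information is collected. Demographics and medical history are recorded at screening (Table 5, Sections 5.1 and 5.6.1). Table 5 schedules "Review of reported baseline symptoms" at Day 1, and daily symptom ratings and SpO2 start then. Section 6.1 says symptom severity is tracked from before the start of treatment on a 0-10 scale.

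Randomisation details are in Section 4.2 of the Master Protocol, and further methods and models are referred to the SAP. Neither document is shown.

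**The concern.** The endpoint is seeking care because symptoms worsen. Age and symptom severity at entry are natural candidates for predicting who will do that. An analysis that ignores them treats predictable between-participant variation as noise. With few events, a visible chance imbalance in either covariate could also make a borderline result awkward to interpret if no adjustment was prespecified.

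The choice is made in the protocol itself. A SAP can add a supporting model, but making an adjusted estimate primary would depart from Section 7.4.2, so the place to decide is the protocol. What is at stake is a little precision, not validity.

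**Working it through.** **Inputs from the protocol.** Event rates 6% and 2.4%, 1:1 allocation, 659 per group, 90% power, pooled chi-square without continuity correction (Section 7.2, Synopsis). Two-sided alpha is taken as 5%, as in the Synopsis and Section 7.4.3. Section 7.2 prints "0.5% significance level", which does not fit the stated size: two-sided 0.5% would need 1036 per group, and 659 would then give only 67% power. That conflict is a separate matter and has more effect on the plan than this one.

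**Step 1: the plan's own figure.** The mean rate is (0.06 + 0.024)/2 = 0.042.

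n per group = [1.960·√(2·0.042·0.958) + 1.282·√(0.06·0.94 + 0.024·0.976)]² / 0.036²
= [1.960·0.2837 + 1.282·0.2825]² / 0.001296 ≈ 651.

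The protocol states 659, which is 1.2% higher. A small allowance for the futility look is a plausible reason, and the figure reproduces.

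Power at 659 = Φ[(0.036·√659 − 1.960·0.2837)/0.2825] = Φ(1.303) = 90.4%. The chi-square delivers the stated power.

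Expected events: 0.042 × 1318 ≈ 55, of which 0.024 × 659 ≈ 16 are in the active arm.

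**Step 2: what adjustment removes.** Let p₁(x) and p₀(x) be the placebo and active risks given a baseline score x. With 1:1 allocation and N participants in total:

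- Unadjusted: N·Var = 2[0.06·0.94 + 0.024·0.976] = 0.1596
- Standardised: N·Var = 2E[p₁(x)(1 − p₁(x))] + 2E[p₀(x)(1 − p₀(x))] + Var[p₁(x) − p₀(x)]
- R = 1 − (standardised / unadjusted)

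**Assumption:** the score is normal on the logit scale, with marginal risks held at 6% and 2.4%. Its strength is not in the documents, so a range is shown. AUC is measured in the placebo arm.

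| AUC of score | Variance removed (R) |
|---|---|
| 0.57 | 0.3% |
| 0.64 | 1.1% |
| 0.70 | 2.6% |
| 0.75 | 4.9% |
| 0.84 | 11.7% |

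**Step 3: convert to power and size.** Replace 659 by 659/(1 − R) in the power formula, and multiply 651 by (1 − R).

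| R | Power at 659 per group | n per group for 90% power |
|---|---|---|
| 0 | 90.4% | 651 |
| 1% | 90.7% | 645 |
| 3% | 91.2% | 632 |
| 5% | 91.7% | 619 |
| 10% | 93.1% | 586 |

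For AUC 0.64 to 0.75 the gain is about 0.3 to 1.4 points of power, equivalent to 6 to 32 participants per group. A gain near 3 points would need an AUC above 0.8.

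**The case against.** The strongest reply is that nothing here is broken. The chi-square is valid under randomisation, its type I error already allows for chance imbalance, it matches the sample-size basis, and it reaches 90% power. All of that stands. A reader might infer that the protocol chose a wrong or underpowered test; Step 1 shows it did not.

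Several narrower objections also stand and limit the claim:

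- **Size.** The gain depends on a prognostic strength the protocol never gives. Nothing in it supports an AUC of 0.80 or more from age and self-rated symptoms.
- **Missing outcomes counted as events.** These imputed events need not follow age or severity, so they would probably weaken the covariate-outcome link. The working models true events only.
- **Timing of the severity score.** Randomisation is at Visit 1 and Day 1 is the date of first intake. No section fixes the Day 1 rating as pre-dose, and one entered after the first dose would be a post-treatment covariate. Age has no such problem.
- **Interim analysis.** Section 7.4.3 uses a chi-square and a futility bound of 0.0232 on the raw difference. A changed final estimator has to be squared with that.
- **Unseen documents.** Stratification factors, if any, are in the Master Protocol. The SAP could hold a supporting adjusted analysis, so one cannot conclude that none is planned anywhere.

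The worry that a logistic model would change the target to a conditional odds ratio does not stand once the model is marginalised to a risk difference. Section 7.1 states its hypotheses as differences in proportions, so the quantity estimated is unchanged.

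**Conclusion.** The point holds as an optional improvement. The unadjusted chi-square is sound, and replacing it as the primary estimate would bring about 1% to 5% less variance and 0.3 to 1.4 points of power. This assumes a logistic-normal baseline score with AUC 0.64 to 0.75, a two-sided 5% level and the planned event rates. The gain would be smaller if many missing outcomes are counted as events.

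It is tempting to call the gain free. The protocol does not support that: it needs a pre-dose definition of severity, a rule for missing baseline values, a short covariate list and a statement about the interim. Low cost is the fair description.

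**What to change.** In Section 7.4.2 and the SAP:

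1. Make the primary estimate a covariate-standardised risk difference: a logistic model with treatment, age and a symptom-severity score, marginalised over the analysis population, with a robust standard error and 95% confidence interval.
2. Define the severity score as a rating recorded before the first dose.
3. Add any stratification factors named in the Master Protocol, and otherwise keep the covariates to these two, given about 55 expected events.
4. State a simple rule for missing baseline values.
5. Keep the pooled chi-square without continuity correction as a supporting analysis.
6. State that the interim futility rule in Section 7.4.3 stays on the raw difference.

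The sample size need not change. The cost is a wording change in protocol and SAP and minor programming. If the sponsor prefers to leave the primary test as it is, naming the standardised risk difference as a prespecified supporting analysis would at least settle the adjustment question before unblinding.

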Group 1	80 mg famotidine (PO) QID + celecoxib 400 mg first dose, followed by 200 mg (PO) BID for 5 days. Following this 5-day period, participants will continue their 80 mg famotidine QID treatment for an additional nine days.	659
Group 2	Matching Placebo for famotidine and celecoxib respectively – QID + BID for five days. Following this 5-day period, participants will continue to receive matching famotidine Placebo, QID, for an additional 9 days.	659

Table 4:Study Interventions

Disclosure Statement: This is a Phase 2 randomized, double-blind, placebo-controlled study to evaluate the safety and efficacy of the combination of famotidine and celecoxib as a post-exposure prophylaxis (PEP) for newly-infected for COVID-19 patients. These participants will not be hospitalized at enrollment, and all study activities will be performed at the participant's home. Investigational product and matching Placebo will be shipped directly to the participant from the Sponsor's supplier. There will be no other physical location where participants are seen. Virtual research teams will be organized by U.S. geographical region under the oversight of a Principal Investigator licensed to practice in the state(s) in which participants reside. Each site or group of affiliated sites will be required to designate at least one physical location to serve as a research facility for storage of any paper documents generated, mail correspondence or location

for inspection activity. This designated location will be listed as a research facility under Section #3 of Form FDA 1572.

Number of Participants: Approximately 1800 participants will be screened to achieve 1465 randomly assigned to study intervention and at least 1318 evaluable participants for an estimated total of 659 evaluable participants per group.

Study Design: The study design is shown schematically in Figure 1.

Schedule of Assessments: The participants will have responsibility for entering self-assessment of symptom severity, body temperature, blood oxygen concentration (spO2) using Sponsor-supplied devices, using the web-based platform. The study Schedule of Assessments is shown in Table 5.

LEAP-CT as a Post-exposure Prophylaxis for Newly-infected COVID-19 Patients

Version 2.0; 11 April 2022

Table 5:Schedule of Assessments

Study Activities and Assessments	Screening & Randomization ¹		Treatment	Period		Observ	ation Period ²
Visit Number ³	1	2	3	4	5	6	7

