5.2. Baseline and Enrollment

Adherence to the study design requirements, including those specified in the SoA, is essential, and required for study conduct.

The following will be performed/collected at Baseline/Day 1:

- Concomitant medication review
- Review of reported baseline symptoms
- Confirmation of Study Drug Receipt & Initial Dose
- Adverse Event Review
- Participant Symptom, SpO2, mobile ECG, & Temperature reporting

Eligibility to continue with dosing of study drug will be confirmed by the Investigator, at Baseline. Should a participant be found to have become ineligible at this time, it will be noted in and the participant discontinued from the study as a Screen failure.

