7.3. Populations for Analyses

For purposes of analysis, populations are defined in Table 8.

Population	Description
Enrolled	All participants that have signed the Informed Consent Form, met the eligibility criteria, were randomized to study intervention, discontinued before first intake (Screening failures) or received at least one of study medication (Intent-To-Treat (ITT), Safety)
Full Analysis (FAS)	All participants who were randomized and received at least one dose of study medication. Participants in the FAS/ITT will be analyzed as randomized.

Table 8:Analysis Populations

Population	Description
Per Protocol (PP)	All participants who were included in the ITT, completed at least the 30-day assessments, and had no major protocol deviations that could have an influence on the primary efficacy endpoint. Participants in the PPS will be analyzed as treated.
Safety	All participants randomly assigned to study intervention and who take at least one dose of study intervention. Participants will be analyzed according to the intervention they actually received.

Participants excluded from the analysis sets mentioned above will be determined during the Blinded Data Review (BDR) and reasons for exclusions will be documented in the BDR report.

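### The stated 90% power is for clinical event rates of 6% vs 2.4%, but the primary test also scores missing Day 30 endpoints as events, which neither the rates nor the sample size allows for

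*Protocol*

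**What the plan says.** **Sample size (Section 7.2).** "A total of 1318 evaluable participants, defined as part of the Full Analysis population (659 per group) are required" to show a fall from 6% on placebo to 2.4% on active with 90% power, using a pooled chi-square test without continuity correction. The Statistical Methods paragraph of the Synopsis describes the 6% as clinical events only: a COVID-19-related medically attended contact or a COVID-19 death by Day 30. The level is printed as "with 0.5% significance level, assuming variances are pooled", whereas the Synopsis and Section 7.4.3 both give two-sided 5%.

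**Inflation.** "Assuming a 10% screen failure rate, 1465 enrolled participants will be required". The Synopsis (Number of Participants) puts it differently: "Approximately 1800 participants will be screened to achieve 1465 randomly assigned to study intervention and at least 1318 evaluable participants". Table 8 (Section 7.3) describes some enrolled participants as "discontinued before first intake (Screening failures". Section 5.2 adds that someone found ineligible at Baseline, which follows randomization, is recorded this way: "the participant discontinued from the study as a Screen failure".

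**Primary analysis (Section 7.4.2).** It is run on the ITT, which Table 8 equates with the FAS: randomized and at least one dose, with no requirement for endpoint data. On missing data, "the primary analysis will consider participants (with missing primary endpoint data until day 30) as having at least one medically attended visit". A complete-case analysis is the sensitivity analysis.

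**Interim (Section 7.4.3).** Participants with a missing Day 30 endpoint are left out. The sample size may be raised if the treatment difference falls by more than 10%. On the final analysis the section says "90% power is kept for the final analysis".

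**The concern.** The test that was powered and the test that was specified are not the same. The power calculation compares 6% with 2.4% and contains no imputed events. The specified test compares these rates plus whatever share of event-free participants lack Day 30 data.

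With event rates this low, a few imputed events matter. When missingness is equal in the two arms, imputation adds nearly the same amount to both rates. The difference barely shrinks, but the variance grows quickly in relative terms. A handful of missing participants per arm can then cost more power than ordinary dropout would.

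At stake is the 90% figure stated for the final analysis in Sections 7.2 and 7.4.3. It describes the complete-case sensitivity analysis rather than the primary one. The trial is fully remote and depends on participants entering their own data, so some missing endpoints should be planned for.

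**Working it through.** **Inputs.** Event rates 6% and 2.4%, 659 per arm, 1:1, pooled chi-square without continuity correction (Synopsis, Section 7.2). Two-sided 5% (Synopsis, Section 7.4.3). Missing rates are my assumptions because the protocol gives none. The futility look is ignored.

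**Step 1: reproduce the plan's figure.** Power = Φ[(d − 1.96·s0)/s1], where d is the difference, s0 = √(2·p̄(1−p̄)/n) and s1 = √((p1(1−p1)+p2(1−p2))/n). With p1 = 0.06, p2 = 0.024 and n = 659: d = 0.036, p̄ = 0.042, s0 = 0.01105, s1 = 0.01101. This gives Φ(1.303) = 90.4%.

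The fixed-design requirement for 90% power is 651 per arm. A non-binding O'Brien-Fleming-type futility look at half the information raises it to about 665. So 659 is reproduced, with nobody missing. At the printed 0.5% level the requirement is 1036 per arm, and 659 gives 67%. Of these two levels, only 5% fits. The inflation also reproduces: 1318/0.90 ≈ 1465.

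**Step 2: apply the rule in Section 7.4.2.** Let m be the share of event-free participants with a missing endpoint. The scored rate is p + (1−p)·m. Example, m = 2%: placebo 0.06 + 0.94 × 0.02 = 7.88%; active 0.024 + 0.976 × 0.02 = 4.35%. Then d = 0.0353, s0 = 0.01320, s1 = 0.01317, and power is Φ(0.714) = 76%.

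| m, equal in both arms | Scored rates | Power, 659 per arm | Complete cases, 659(1−m) per arm | Power, 732 per arm |
|---|---|---|---|---|
| 0% | 6.0 vs 2.4% | 90% | 90% | 93% |
| 1% | 6.9 vs 3.4% | 83% | 90% | 87% |
| 2% | 7.9 vs 4.4% | 76% | 90% | 80% |
| 5% | 10.7 vs 7.3% | 58% | 89% | 63% |
| 10% | 15.4 vs 12.2% | 40% | 87% | 44% |

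The complete-case column assumes missingness unrelated to outcome. It shows that the loss comes from the imputation rule and not from losing participants. Power at 659 per arm drops below 80% at m of about 1.5%, or roughly 9 event-free participants per arm (placebo: 659 × 0.94 × 0.0147 ≈ 9.1).

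**Step 3: does the 10% margin cover it?** Table 8 and Section 5.2 place screening failures before or at first dose, outside the FAS. The account that fits Sections 5.2, 7.2, 7.3 and the Synopsis is 1465 randomized, 10% never dosed and 1318 in the FAS, with missing endpoints arising among those 1318. Suppose instead that all 1465 entered the FAS (about 732 per arm). Power would still be 87% at 1% missing and 80% at 2%.

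**Step 4: when missing participants truly had events.** They are scored correctly and cost nothing. With 2% missing, half of them true events, the rates are 7.0% vs 3.4% and power at 659 per arm is 84%.

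**Step 5: unequal missingness (659 per arm).** Placebo 3%, active 2%: 8.82% vs 4.35%, power 91%. Placebo 1%, active 2%: 6.94% vs 4.35%, power 53%.

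**Step 6: would the interim check show the loss?** The interim excludes missing participants, so its expected difference stays at 3.6 points when missingness is unrelated to outcome. Even with imputed events counted, equal missingness gives a difference of (1−m) × 3.6 points. A fall of more than 10% then needs m above 10%, where power is already about 40%.

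**The case against.** The strongest reply is that scoring missing as an event is a deliberate conservative rule, with a complete-case analysis already planned beside it. That stands. The primary test is not invalid, and the protocol may keep it. What needs correcting is the power figure attached to it.

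A second reply is that the loss rests on missing rates the protocol never states, and that the conduct provisions limit missingness: daily data entry, documented contact attempts, and continued follow-up after study drug is stopped. This also stands, and it is why the figures are given as a range.

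Three stronger readings are tempting, and the documents do not support them.

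- A reader might infer that power is certain to fall below 90%. That holds only for equal missingness among event-free participants; with more missing on placebo than on active, power can stay at 90% or rise above it.
- A reader might take the 147 participants between 1465 and 1318 as dosed and then missing, which gives about 44% power. This needs all 147 to be in the FAS, against the screen-failure label and the wording of Table 8 and Section 5.2.
- A reader might say the DSMB depends on the 90%. The Synopsis gives it a safety-monitoring role, and its detailed activities are in the Master Protocol, which is not at hand.

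The different rule at the interim does not threaten the type I error either, because the futility bound is non-binding. Using the final rule unaltered at the interim would be wrong if it scored participants who have not yet reached Day 30 as events.

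**Conclusion.** The mismatch is real. The 90% in Sections 7.2 and 7.4.3 belongs to a test with no imputed events, and Section 7.4.2 specifies a test that has them. Under equal missingness among event-free participants, 1 to 2% missing takes power at 659 per arm to 83 or 76%, and 5% takes it to 58%. The loss is smaller where missing participants truly had events, and unequal missingness can move power in either direction. All of this assumes two-sided 5%, the protocol's 6% and 2.4%, and the normal approximation, with the futility look set aside. No missing rate is documented, so no single figure can be called the trial's power.

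This should be fixed. It is an error in a stated operating characteristic, not a flaw that invalidates the primary analysis.

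**What to change.** 1. In Section 7.2, restate the power for the missing-as-event rule over a stated range of equal and unequal missing rates, and give the lower power plainly. Amend the matching sentence in Section 7.4.3.
2. In Section 7.2, correct the significance level from 0.5% to the two-sided 5% of the Synopsis and Section 7.4.3.
3. In Section 7.2, say that the 10% margin covers losses before first dose and not missing endpoints. Reconcile this with the Synopsis paragraph on participant numbers and with Table 8.
4. In the interim sample-size check, also look at the rate of truly missing endpoints: participants past the Day 30 window without data, not those still to reach it.

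The cost is a rewritten power paragraph and a few lines in Section 7.4.3. No change to the sample size is required if the lower power is stated. Keeping 90% under this rule would take about 808 per arm at 1% equal missingness, 968 at 2% and 1468 at 5% (fixed design). Moving missing-as-event to a sensitivity analysis is an option only; a complete-case primary would rest on a missing-at-random assumption.
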